10.5 Adverse Event Outcome

The outcome of AEs will be recorded as follows:

- *Resolved*: The event is considered fully resolved.
- *Continuing*: At study exit the event is considered ongoing.

Note: Any unresolved AE ongoing past study exit will be monitored by the physician per institutional standard of care.

10.6 ADVERSE EVENT RECORDING

AEs will be documented in the applicable source documentation (i.e. medical record). Study data collection forms should capture the event diagnosis as opposed to symptoms (e.g. Infection vs. fever). The adverse events of pneumothorax and bronchopulmonary hemorrhage (including hemoptysis) will be documented as follows:

- *Hemorrhage*: Significant bronchopulmonary hemorrhage including hemoptysis will be defined as bleeding noted at the time of procedure that requires a change in the level of care (e.g. outpatient to inpatient or inpatient to ICU) or a blood transfusion or separate intervention (i.e. surgery or embolization). Severity will be classified according to CTCAE as follows:
 - *Grade 1*: Mild symptoms; intervention not indicated
 - *Grade 2*: Moderate symptoms; medical intervention indicated
 - *Grade 3*: Transfusion, radiologic, endoscopic, or operative intervention indicated (e.g. hemostasis of bleeding site)
 - *Grade 4*: Life-threatening respiratory or hemodynamic compromise; intubation or urgent intervention indicated
 - *Grade 5*: Death

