OBJECTIVES	
The registry is aimed developing a high-quality set of data regarding intraoperative percutaneous localization of peripheral pulmonary nodules (PPNs), and then identifying and promulgating efficient, evidence-based best practices for this technique. The resection procedure itself is standard of care and follows the investigator's standard protocol.
 
Successful localization of PPNs is a challenge involving multiple factors, beginning with the subjects' health, lung function and also factors specific to the nodule including location within the lung, size, distance from the lung surface, whether solid or ground glass and proximity to a fissure. Hard to see or palpate nodules are currently localized with dye and/or hook wires or fiducials, either endoscopically or percutaneously. Successful, large, prospective studies have not been reported using modern electro-magnetic navigation (EMN)-guided percutaneous intraoperative localization, and different techniques (dye vs. fiducial vs. hook wire etc.) have not been evaluated. It is for these reasons that the different localization techniques used with EMN-guided percutaneous localization will be collected for patients having a suspicious nodule and who undergo percutaneous intra-operative localization and immediate resection.
 
This registry aims to record the localization techniques used by thoracic surgeons and IP/surgical teams to identify PPNs using the SPiN Thoracic Navigation System™ in the hands of trained physicians. The objectives of this study will be to accomplish the

	primary and secondary objectives listed below, and to observe localization in a real-world context of pulmonary resection.
PRIMARY OBJECTIVE	Successful percutaneous localization of PPN. This is defined as the percentage of subjects in whom the nodule is successfully localized and removed in the first resected specimen. A pathological specimen with clear margins will count as a successful localization.
SAFETY OBJECTIVES	
1. Report the incidence of device-related adverse events that occur during the localization procedure.

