Results from studies involving procedural guidance technologies such as electromagnetic navigation (EMN) and radial endobronchial ultrasound (radial EBUS) have also been reported (Ost *et al.*, 2016). Diagnostic yield was reported at 57% with r-EBUS alone, 47.1% with EMN combined with r-EBUS. In another recent study published in the New England Journal of Medicine, a total of 639 subjects underwent bronchoscopy for suspected lung cancer and of those bronchoscopic examinations, 43% were nondiagnostic, including in 25% (120 of 487 subjects) in whom lung cancer was ultimately diagnosed (Silvestri *et al*, 2014). As a result of published yields showing an unacceptable yield for peripheral bronchoscopy, ACCP guidelines recommends that nodules without a CT-bronchus sign should be pursued with EMB-TTNA (Rivera *et al*, 2013).

A prospective, single center pilot study evaluated the safety, feasibility, and diagnostic yield of staged approached for taking biopsy samples in a single procedure setting (Yarmus LB et al., 2016). In this study, enrolled subjects (n=24) underwent EBUS for lymph node staging, followed by EMN-bronchoscopy, and EMN-TTNA. The researchers report a diagnostic yield of 83% for EMN-TTNA alone, and 87% when combined with EMN-bronchoscopy. The diagnostic yield increased to 92% when combined with EBUS. There were five (21%) pneumothoraces of which two (8%) required chest tube placement. No bleeding events were observed. The researchers conclude that the results demonstrate an acceptable safety and feasibility profile.

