8.2.3 Trans-thoracic Nodule Localization – Registry Procedure

The risks associated with trans-thoracic nodule localization are bleeding and pneumothorax,

The measures to mitigate the risks are the same for all surgical procedures. Patients are given supplemental oxygen and their oxygen level is continuously monitored using pulse oximetry. A nurse or physician continuously monitor patients' ECG, heart rate, blood pressure, and blood oxygen during the procedure.

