9. RESEARCH METHODS AND DATA COLLECTION

In this study, the “lung resection and after care protocol” is determined by each investigator’s current practice, with an outline provided in the registry to explain the context for the type of data collection performed in this patient population. The medical device is being marketed for and used within its intended use.

Localization methods and outcomes, and data related to the nodules, diagnosis, and the setting of the planned clinical intervention of nodule removal will be recorded. Data will be collected according to descriptions below, Table 1 and Figure 1.

Collected data include brief medical history, smoking history, demographic characteristics, radiographic characteristics, procedural characteristics, crossover to other procedures, and adverse events, as follows:

- *Radiographic Characteristics:*

The location of the target nodule (side, lobe and segment, i.e. right upper lobe anterior segment, etc.) will be determined and recorded. The radiographic information collected from CT will include size of the nodule (longest axis), distance from a visible bronchus, and distance from the pleural surface perpendicular to the nodule.

- *Procedural Characteristics:*

Collected procedural information will include the distance of target from pleura nodule statistics (volume, RESIST diameter, maximum, minimum, and effective diameter), and target motion. The duration of the localization procedure will also be recorded.

- *Crossover to Other Procedures:*

All procedures performed to aid in the surgical management of patients – will be noted. Wedge resection, segmentectomy, and lobectomy. The type of initial surgery planned, and the eventual surgery done, will both be collected.

- *Adverse Events:*
All device and/or procedure related adverse events will be recorded for the study localization procedure. Events will be collected from the initiation of the localization procedure to the start of the wedge resection procedure. Study sites will report localization-related adverse events and complications to their IRBs according to institutional requirements. These will be recorded.

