If the nodule is fully removed in crossover cases, then the primary endpoint is met. The nodule may be removed per the surgeon's judgement. The pathology findings will then identify the entire case as either benign or malignant, and the primary endpoint is met.

If Diagnosis is Non-malignant

If the nodule is deemed non-malignant, cells are identifiable, then the positive box for diagnosis is checked, and:

- The nodule must have an intact margin of a cell as a perimeter to be diagnostic.
- The type of nodule (ground glass opacity, etc.) is collected from the pathology report.

The pathology findings will then identify the case as either benign or malignant.

9.3 Safety Objective:

Record Safety Events During Intraoperative Percutaneous Localization Only

To collect and evaluate the safety of nodule localization, including incidence and severity of localization-procedure related adverse events (AEs) and serious adverse events (SAEs) that occur during the localization procedure.

Baseline/Enrollment

All patients will be provided with information about the registry and will sign the informed consent form before any registry-related assessments are made. The following data will be collected at baseline for all enrolled patients:

- To be collected at baseline visit: Review of inclusion/exclusion criteria.

Localization Period

- The localization period begins when the needle touches the subject's skin.
- Localization ends when the localization needle is withdrawn from the subject for the final time.
- Any adverse events that develop during the localization procedure will be reported.
- Bronchoscopy-related events that occur during the alignment of the CT with the patient ("registration") will be recorded.
- Percutaneous localization step, injection of dye, injection of any microcoils, etc.

The process used for AE reporting conforms to Veran Medical Technologies, Inc., standard operating procedures (SOPs) for Medical Device Reporting (MDR)(Appendix C). Training on AE/SAE/MDR reporting practices will be provided to each participating site.

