9.9 Nodule Localization

The bronchoscope (Olympus MP-160 or BF-190) will be introduced into the airway. A Veran tip tracked instrument will then be introduced into the working channel of the bronchoscope and utilizing standard Veran System navigation-matching protocols, the main and secondary carinas are identified using the tip tracked instrument to confirm that the Veran System is properly matched to the airway defined by accurate matching of the main and secondary carina. This allows the system to align the CT with the patient's current position.

Following registration, a sterile field is created on the chest wall as identified by the Spin Perc planning software and the area is prepped and draped. A tip tracked needle, such as one of the Veran localization needles or the Veran tip tracked Spin Perc needle introducer, is selected. The surgeon advances the needle trans thoracically into the nodule, under Veran EMN guidance, to the nodule. The nodule is localized percutaneously by marking with dye using an assortment of tools designed for this purpose (Section 5.1), adding microcoils or fiducials, etc.

Data Collected: patient position, registration, volume of dye, type of dye, use of microcoils or fiducials.

The surgeon then continues to wedge resection, and the registry portion of the procedure is completed.

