10.3 Adverse Events – Data Collection for Localization Events

An adverse event (AE) is any untoward medical occurrence, unintended disease or injury, or untoward clinical signs (including abnormal laboratory findings) in subjects, users or other persons, whether or not related to the investigational medical device. Note: Pre-existing conditions are not considered to be adverse events unless there is a change in the nature or severity of the condition.

We will collect data on the localization adverse event through subject discharge from hospital. Principal Investigators were taught to use FDA 3500A MedWatch (Appendix C) and were taught to fill those out during the investigator meeting, for relevant SAEs and also for medical device complaints. This registry's primary safety objective is to collect localization-related safety events in patients undergoing localization prior to wedgeectomy.

The Medical Device Reporting (MDR) regulation (21 CFR 803) contains mandatory requirements for device user facilities (including hospitals, surgical facilities and other) to report certain device-related serious adverse events and product problems to the FDA. These are described in the forms in Appendix C, and the FDA's Guidance for User Facilities.

- User facilities must report a suspected medical device-related death to both the FDA and the manufacturer within 10 days.
- User facilities must also report a medical device-related serious injury to the manufacturer (Veran Medical Technologies, address below).
- In addition, each IRB and institution may have its own policies regarding the content, format, and timing for the reporting of safety information.

¹ The Electronic Code of Federal Regulations (www.ecfr.gov) - <https://www.ecfr.gov/cgi-bin/textidx?SID=244dabc113521b0a851a5db147554fdd&mc=true&node=pt21.1.50&rgn=div5> accessed 4/16/2019.

Each investigator or delegate is responsible for fulfilling these duties.
Please report device serious adverse events to Veran as noted below on form 3500A
(Appendix C).

Please scan and send completed forms to:
Email: [contact]
Email: [contact]

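### Section 10.6 announces a documentation rule for pneumothorax but gives one only for hemorrhage; with immediate resection and three different adverse-event windows, the pneumothorax incidence will be hard to interpret and is probably undercounted under the two shorter windows

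*Combined protocol and SAP*

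**What the plan says.** Section 8.2.3 names two risks of the needle step: "The risks associated with trans-thoracic nodule localization are bleeding and pneumothorax". Section 10.6 then states: "The adverse events of pneumothorax and bronchopulmonary hemorrhage (including hemoptysis) will be documented as follows". What follows is a hemorrhage definition with Grades 1 to 5, and Section 11 begins directly after it. At that point there is no redaction mark or visible gap. No pneumothorax definition, method of detection, time point or severity scale appears elsewhere in the text.

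The synopsis gives one safety objective: "Report the incidence of device-related adverse events that occur during the localization procedure". Section 9.3 (Safety Objective) widens it to events related to the localization procedure.

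The end of collection is stated three ways:

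- Section 9.3, Localization Period: "Localization ends when the localization needle is withdrawn from the subject for the final time".
- Section 9, Adverse Events: "Events will be collected from the initiation of the localization procedure to the start of the wedge resection procedure".
- Section 10.3: "We will collect data on the localization adverse event through subject discharge from hospital".

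On sequence, Section 9.9 says: "The surgeon then continues to wedge resection, and the registry portion of the procedure is completed". It describes no check for pneumothorax between the two steps. Its list of collected data covers patient position, registration, dye and markers.

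The only pneumothorax rate in the document is in Section 7, from a pilot of 24 subjects who had navigated needle aspiration for diagnosis: "There were five (21%) pneumothoraces of which two (8%) required chest tube placement".

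**The concern.** The gap affects the result because of the sequence of the operation. Resection is by VATS, RATS or thoracotomy, each of which lets air into the pleural space. After chest entry, a needle pneumothorax that caused no physiological change can no longer readily be told from surgical air. It can be recognised only before entry or at the moment of entry, and the plan asks for neither observation.

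Sites following the protocol could therefore record the same finding differently. One might count any lung found already down at entry. Another might treat entry as outside the period and record nothing. A third might use the discharge window and attribute postoperative air to the needle.

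Localization-event incidence is the registry's only safety objective. A low figure that partly reflects non-detection could be read as evidence of safety, and a high one could partly reflect the operation. The reported number would not show which.

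**Working it through.** **1. What the general rules cover.** Section 10.3 defines an adverse event. Section 10.4 offers related, not related and undetermined, with relatedness resting on plausible timing. Section 10.6 asks for diagnoses rather than symptoms. Section 11.2.1 codes all events with CTCAE. These rules classify an event once someone has noticed it. None says when or how to look, or how to separate needle air from surgical air.

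**2. The three windows set against a silent needle pneumothorax.**

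- To needle withdrawal: first chest entry falls outside, so a finding there is not clearly recordable.
- To the start of wedge resection: whether first chest entry falls inside is unclear.
- Through discharge: entry falls inside, but so does all surgical air, and a temporal causality rule does not separate the two.

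**3. The document's own figure.** 5/24 = 20.8% (stated as 21%) and 2/24 = 8.3% (stated as 8%). Both reproduce. The exact (Clopper-Pearson) 95% interval for 5/24 is 7.1% to 42.2%.

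**4. Scale at the registry's size** (70 to 100 evaluable, Section 11.1). Expected events are 70 × 5/24 = 14.6 and 100 × 5/24 = 20.8, about 15 and 21.

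**5. Effect of incomplete recording.** Let s be the share of needle pneumothoraces that is recorded. The document does not give s, so the whole range is an assumption. Recorded rate = s × 5/24.

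| s | Recorded rate | Expected of 70 | Expected of 100 |
|---|---|---|---|
| 0% | 0% | 0 | 0 |
| 10% | 2.1% | 1.5 | 2.1 |
| 25% | 5.2% | 3.6 | 5.2 |
| 40% | 8.3% | 5.8 | 8.3 |
| 75% | 15.6% | 10.9 | 15.6 |
| 100% | 20.8% | 14.6 | 20.8 |

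The 40% row is the pilot's chest-tube share, 2 of 5.

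Exact 95% intervals at whole counts:

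- 0/70: 0 to 5.1%; 0/100: 0 to 3.6%. Both upper limits lie below the pilot's lower limit of 7.1%.
- 4/70 = 5.7%: 1.6 to 14.0%.
- 6/70 = 8.6%: 3.2 to 17.7%.
- 15/70 = 21.4%: 12.5 to 32.9%.

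The intervals for 4/70 and 6/70 exclude 20.8% but overlap the pilot's own interval.

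**6. How likely is a count of zero?** P(0) = (1 − s × 5/24)^N. At s = 10% this is 23% for N = 70 and 12% for N = 100. At s = 25% it is 2.4% and 0.5%. A result near zero therefore needs s of about 10% or less.

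**7. Over-attribution.** Let f be the share of subjects without a needle pneumothorax who nevertheless have one recorded, also an assumption. Recorded rate = s × 5/24 + f × 19/24. This equals 5/24 when f = (1 − s) × 5/19: 24% at s = 10%, 20% at s = 25% and 16% at s = 40%. Above those values the count is too high.

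**The case against.** The strongest reply is that pneumothorax is not left without rules. The general adverse-event, seriousness, causality, outcome and CTCAE provisions all apply to it, and nothing excludes it from the count. Section 8.2.3 describes continuous monitoring of ECG, heart rate, blood pressure and oxygen, which could reveal a pneumothorax with physiological effect. Safety is deliberately limited to the localization step, no hypothesis is tested, and no comparison with the pilot is planned. The pilot was diagnostic aspiration in 24 subjects. Section 10.2 refers to an appendix for all data elements; its content and the eCRF were not supplied, and either could hold a pneumothorax field.

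Most of this stands, and it limits the point. A reader might infer that the protocol has no rule of any kind for pneumothorax; the general provisions contradict that. A reader might also infer that the count will be near zero by construction and the incidence necessarily biased low. That does not follow either: the recorded share is undocumented, and the discharge window could push the count upward through misattribution.

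The reply does not supply a time or method of ascertainment. Monitoring does not reach silent events, and in the pilot 3 of 5 pneumothoraces needed no chest tube. A longer window cannot recover what chest entry has masked. It is also fair to say that the document does not show how often lung collapse can be judged at first entry, so that observation may often be unavailable.

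**Conclusion.** The point holds as a gap in ascertainment and attribution. Section 10.6 lacks the pneumothorax entry that it announces, and three conflicting windows leave each site to decide what counts. Undercounting is probable under the two shorter windows, over-attribution is possible under the discharge window, and variation between sites is plausible under any of them.

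The size cannot be fixed from the document. At the pilot rate, the reported figure could lie anywhere from 0% to 20.8% depending only on the share recorded, and higher if surgical air is attributed to the needle. This rests on assumed values of s and f and on a pilot rate used for scale only. A pneumothorax field in the unseen eCRF would narrow the gap, but would not by itself reconcile the windows. The change should be made, because it bears on the registry's only safety objective.

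**What to change.** Add the announced pneumothorax entry to Section 10.6, as a recording rule only:

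- (a) Recognised before chest entry: yes/no, with CTCAE grade.
- (b) At first chest entry, lung already down: yes/no/not assessable (for example, lung isolation already started).
- Air leak at the needle puncture as a separate item, since a leak is not itself a pneumothorax.

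Report (a) over all localized subjects and (b) over assessable subjects, with the number not assessable. State that air caused by the resection is not counted, and that the rate is not comparable with imaging-detected rates from biopsy studies.

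Reconcile the windows in Section 9 (Adverse Events), Section 9.3 (Localization Period) and Section 10.3, and say explicitly whether the finding at first chest entry falls inside. If the eCRF already holds a pneumothorax field, align it with this entry.

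The cost is a few eCRF fields and a few lines of protocol text, with no added imaging, procedure or staff. The downside is a possibly less favourable rate and a not-assessable group that may be large.

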11. STATISTICAL METHODS

11.1 Sample Size

This is an observational study where no formal hypothesis is being tested, data collected during the study will be summarized using descriptive statistics. No formal sample size estimations were utilized to determine the size of the study population. Generally, demographic and other descriptive characteristics of the cohorts will be described as counts and percentages for categorical variables and as measures of central tendency (mean, median, standard deviation [SD], and range) for continuous variables. Ninety-five percent (95%) confidence intervals will be computed for measures of effect and association. In some cases, data may be summarized by demographic.

The study will have 70-100 evaluable patients from approximately 5 sites in the US who undergo percutaneous localization followed by surgical resection. Evaluable patients are those who undergo the percutaneous nodule localization procedure and meet the inclusion/exclusion criteria. Each site will be expected to enroll a minimum of 6 subjects at their site.

11.2 Data Analyses

11.2.1 General Considerations

The analysis to be performed will be described in a written and approved statistical analysis plan (SAP). No adjustments will be made for multiple comparisons.

Effectiveness data will be summarized. Serious adverse events (SAEs) and adverse

events will be listed and summarized. Data collected during the study will be uploaded at the sites into Medrio and summarized and analyzed at least bi-annually.

All AE and Medical History verbatim terms will be recorded and coded using the CTCAE criteria.

